11. STATISTICAL CONSIDERATIONS

General statistical considerations: descriptive summaries will be presented using mean with standard deviation (SD), median, minimum and maximum for continuous variables and as count and percent of subjects for categorical variables. Inferential statistical tests will be two-sided and use alpha (α) of 0.05 as a critical value, unless noted otherwise. Statistical analysis will be carried out using SAS Version 9.4 or later and/or R software language.

11.1. Statistical Power and Sample Size Determination

Overall study sample size is designed to provide adequate power for the primary effectiveness endpoint, at both the interim and final analysis, the key secondary endpoints, and selected secondary endpoints.

As noted above ([Section 6.2](#)), to maintain the balance between sites in terms of numbers of subjects randomized, study sites will be capped at randomizing a maximum of 15% of the overall study sample (i.e., 18 subjects). For sites with a total enrollment consisting of only one type of DOAC drug as per chance, the randomization cap will be replaced by a maximum of 10% of the overall study sample

(i.e., 12 subjects).

The null hypothesis for the primary composite endpoint is represented by:

H_0 : The distributions of the components are the same in the two treatment groups

The alternative hypothesis for the primary composite endpoint is represented by:

H_A : For at least one component, the distribution is different between the treatment groups

The null hypothesis for the first key secondary endpoint is represented by:

$H_0: \pi_{DS} = \pi_{SOC}$

The alternative hypothesis for the first key secondary endpoint is represented by:

$H_A: \pi_{DS} \neq \pi_{SOC}$

where $\pi_{1,DS}$ and $\pi_{1,SOC}$ are the pre-CPB vs. post-CPB mean percent changes in blood apixaban levels with DrugSorb-ATR (DS) and Control (SOC), respectively. The second key secondary endpoint null and alternative hypotheses take the same form as the first key secondary endpoint but substituting rivaroxaban for apixaban.

The null hypothesis for the first secondary endpoint is represented by:

$H_0: \pi_{DS} = \pi_{SOC}$

The alternative hypothesis for the first secondary endpoint is represented by:

$H_A: \pi_{DS} \neq \pi_{SOC}$

where π_{DS} and π_{SOC} are the mean 24-hour CTD volumes with DrugSorb-ATR (DS) and Control (SOC), respectively. The following additional secondary endpoints, for which power is formally allocated (see below), take the same form of null and alternative hypotheses as above: platelet transfusions (mean number of units) and pRBC transfusions (mean number of units).

Approximately 120 combined DOAC subjects meeting the study inclusion criteria ([Section 4.4.1](#)) will be randomized in a 1:1 ratio to the treatment and control arms. A combined DOAC population is planned for analysis in the current study since apixaban and rivaroxaban share the same mechanism of action, same indications for use, same risk for post-surgical bleeding outcomes, have been shown in *ex vivo* testing to have nearly identical removal rates when treated with the study device, and are therefore considered exchangeable.

In terms of the composite primary effectiveness bleeding endpoint, while bleeding is known to be of significant risk in patients on both apixaban and rivaroxaban undergoing CT surgery without preoperative washout, literature quantifying postoperative bleeding outcomes is limited in this specific population. However, published real-world use experience from the Asklepios Klinik St. Georg research group (Hamburg, Germany) has demonstrated highly similar treatment effects for intraoperative CytoSorb® removal of ticagrelor and rivaroxaban in patients undergoing emergent CT surgery. [12] The difference between treatment and control groups regarding postoperative blood loss (in the form of 24hr chest tube drainage volume), reoperation rates for bleeding, and transfusion volumes were comparable between the ticagrelor and rivaroxaban cohorts. Thus, for the purpose of this study, we will anticipate the same treatment effects for DrugSorb-ATR therapy in subjects

undergoing CT surgery (within 36 hours of last DOAC dose) as were utilized for the STAR-T trial (which enrolled subjects undergoing CT surgery within 48 hours of last ticagrelor dose). The difference in timing between last drug dose and start of surgery for the DOAC vs. ticagrelor studies is necessary due to the difference in recommended washout periods between the DOACs and ticagrelor.

Because of exchangeability between apixaban and rivaroxaban, the anticipated proportions of individual DOACs expected in the trial (ranging from 40% - 60%, reflective of real-world use patterns), are not assumed to impact power or sample size. Assuming a 5% dropout rate, a total of 114 subjects (57 per arm) are expected to be evaluable for effectiveness and safety. Sample size is based on published response rates for the primary effectiveness Win Ratio sub-components, as noted for rivaroxaban and ticagrelor (above) with a bridge to apixaban, and can be calculated via an iterative simulation process with programming code available in an appendix to Redfors et al. (2019). [16] As a sensitivity exercise, power was estimated under varying conditions where the ratios of apixaban to rivaroxaban subjects were allowed to range from 40% to 60%, for either drug, and under assumptions of +/-5% worse vs. better outcomes for apixaban as compared to rivaroxaban (see **Table 3**). Power for the study to reject a false null hypothesis is formally estimated where apixaban is assumed equally comparable to rivaroxaban, at a subject ratio of 50:50 (see **bold** results in **Table 3**, below).

Table 3. Win Ratio Effect Size Assumptions with Power and Sample Size Estimates Under Varying Conditions

A:R* Com- para- bility	Ratio A:R	n Per Group	Effect Size						Power	
			Component #1		Component #2		Component #3			
			Fatal Bleeding	UDPB (Class ≥2)	Treatment Event	Control Event	Treatment Event	Control Event		
A Has 5% Higher Event Rate Than R Among Treated Subjects	40:60	Interim Analysis N=39	3.06%	3.00%	24.79%	40.50%	489.6 (253)	800 (253)	88.1%	
	40:60	End of study N=56	3.06%	3.00%	24.79%	40.50%	489.6 (253)	800 (253)	99.3%	
	50:50	Interim Analysis N=39	3.07%	3.00%	24.91%	40.50%	492.0 (253)	800 (253)	87.1%	
	50:50	End of study N=56	3.07%	3.00%	24.91%	40.50%	492.0 (253)	800 (253)	99.2%	
	60:40	Interim Analysis N=39	3.09%	3.00%	25.03%	40.50%	494.4 (253)	800 (253)	86.0%	
	60:40	End of study N=56	3.09%	3.00%	25.03%	40.50%	494.4 (253)	800 (253)	99.2%	
A = R Event Rate Among Treated Subjects	40:60	Interim Analysis N=39	3.00%	3.00%	24.30%	40.50%	480 (253)	800 (253)	91.3%	
	40:60	End of study N=56	3.00%	3.00%	24.30%	40.50%	480 (253)	800 (253)	99.5%	
	50:50	Interim Analysis N=39	3.00%	3.00%	24.30%	40.50%	480 (253)	800 (253)	91.3%	
	50:50	End of study N=56	3.00%	3.00%	24.30%	40.50%	480 (253)	800 (253)	99.5%	
	60:40	Interim Analysis N=39	3.00%	3.00%	24.30%	40.50%	480 (253)	800 (253)	91.3%	
	60:40	End of study N=56	3.00%	3.00%	24.30%	40.50%	480 (253)	800 (253)	99.5%	
A Has 5% Lower Event Rate Than R Among Treated Subjects	40:60	Interim Analysis N=39	2.94%	3.00%	23.81%	40.50%	470.4 (253)	800 (253)	93.6%	
	40:60	End of study N=56	2.94%	3.00%	23.81%	40.50%	470.4 (253)	800 (253)	99.7%	
	50:50	Interim Analysis N=39	2.93%	3.00%	23.69%	40.50%	468.0 (253)	800 (253)	94.2%	
	50:50	End of study N=56	2.93%	3.00%	23.69%	40.50%	468.0 (253)	800 (253)	99.7%	
	60:40	Interim Analysis N=39	2.91%	3.00%	23.57%	40.50%	456.6 (253)	800 (253)	94.7%	
	60:40	End of study N=56	2.91%	3.00%	23.57%	40.50%	456.6 (253)	800 (253)	99.8%	

* A, R = apixaban, rivaroxaban.

Notes: n = number; UDPB = Universal Definition of Perioperative Bleeding; CTD = chest tube drainage (volume [mL]).

Component #1 minimum rates of 3.0% assumed as a conservative approach.

Component #2 rates based on Russo et al. (2019), however, with a discount applied to bring the Treatment arm up to ~40% reduction on the Control arm. [42]

Component #3 rates based on Hassan et al. (2019), however, with a discount applied to bring the Treatment arm up to ~40% reduction on the Control arm. [12]

Using a Finkelstein – Schoenfeld test, a total of 57 subjects per arm ensures power of >99.2% for the primary effectiveness endpoint at the final analysis, using a two-sided alpha (α) of 0.05, and assuming an interim analysis for efficacy at 70% completion. [15] Power for each of the key secondary endpoints is estimated at 96.3% assuming a $40\% \pm 40\%$ mean difference between treatment and control, where N=29 subjects receiving apixaban with N=29 corresponding controls along with parallel numbers of subjects receive rivaroxaban and corresponding control, based on a two-sample t-test assuming equal variance and a two-sided alpha of 0.05. For the 24-hour CTD secondary endpoint, assuming a treatment arm volume of 480 ± 253 mL and control arm volume of 800 ± 253 mL [12] [a discount is applied (see **Table 3** for details) to bring the Active arm up to ~40% reduction on the Control arm], power is similarly estimated at >99.9%. Power for comparisons of platelet transfusions between the treatment arm (0.32 ± 0.9 units) and control arm (1.6 ± 2.2 units) [43] is estimated at 98.0%, based on a two-sample t-test assuming unequal variance and a two-sided alpha of 0.05. Similarly, power for PRBC transfusions between the treatment arm (1.3 ± 2.1 units) and control arm (4.4 ± 5.7) [43] is estimated at 96.7%. Sample size and power for all secondary endpoints were calculated using PASS 2021 (NCSS, LLC. Kaysville, UT, USA, ncss.com/software/pass).

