The primary effectiveness endpoint will be evaluated using the Win Ratio method of analysis for a hierarchical composite endpoint based on the Finkelstein-Schoenfeld test (Finkelstein and Schoenfeld, 1999; Pocock, et al., 2012) with three components: a) fatal bleeding events occurring within 48hrs of the index procedure, b) moderate, severe, or massive bleeding based on the Universal Definition of Perioperative Bleeding in Cardiac Surgery (UDPB) ≥ 2 classification, and c) 24-hour chest tube drainage (volume, mL). The Win Ratio assigns “wins”, “losses”, or “ties” between randomized groups in a serial fashion across all components of the composite endpoint adhering to the declared hierarchical order from higher to lower clinical importance.[14] [15] A ratio of “wins” greater than 1.0 favors the treatment arm; when the lower bound of a 95% confidence interval (CI) around the ratio exceeds 1.0, the treatment is shown to be statistically superior to control at alpha = 0.05. The primary effectiveness analysis will be performed in the overall study population comprised of both apixaban and rivaroxaban patients to evaluate the difference between the SOC (control) arm and the DrugSorb-ATR (investigational) arm.

The key secondary effectiveness endpoints are the pre-CPB vs. post-CPB change in drug levels (apixaban and/or rivaroxaban) measured by liquid chromatography/tandem mass spectrometry (LC/MS-MS) [drug removal endpoint]. Change in each subject's blood concentration of apixaban or rivaroxaban from immediately *before* to immediately *after* CPB will be collected and analyzed by a central core laboratory. Drug removal will be analyzed for apixaban and rivaroxaban independently.

Change from baseline in blood concentration of apixaban or rivaroxaban is defined as:

$$\frac{\text{pre-CPB [apixaban]}_{\text{blood}} - \text{post-CPB [apixaban]}_{\text{blood}}}{\text{pre-CPB [apixaban]}_{\text{blood}}} * 100\%$$

or

$$\frac{\text{pre-CPB [rivaroxaban]}_{\text{blood}} - \text{post-CPB [rivaroxaban]}_{\text{blood}}}{\text{pre-CPB [rivaroxaban]}_{\text{blood}}} * 100\%$$

Based on existing benchtop evidence, a conservative estimate of 40% reduction in blood concentration of DOAC between pre- and post- DrugSorb-ATR removal is expected, with a standard deviation of 40%, in the treatment arm. Minimal change is expected in the control arm. A two-sample t-test will be used to evaluate the difference between treatment arms.

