Additional powered secondary endpoints include 24-hour CTD (volume [mL]), total platelet transfusions (volume [mL] and units), and total PRBC transfusions (volume [mL] and units) during the index hospitalization. Twenty-four-hour CTD (mL) will be assessed via two-sample t-test for mean difference. The transfusion endpoints will all be analyzed using two-sample t-tests for mean differences, and Fisher-Freeman-Halton exact tests for units. In the event the assumptions for a two-sample t-test are not met in any of the above, a nonparametric test such as a Mann-Whitney test will be employed, with median and range values provided in the output. An additional analysis of 24-hour CTD will compare the frequency of subjects falling into volume categories (i.e., <500 mL, 500 to <750 mL, 750 to <1000 mL, 1000 to <1250 mL, 1250 to <1500 mL, and ≥ 1500 mL), and will use a Fisher-Freeman-Halton exact test to compare treatment groups. Other secondary endpoints include the remaining Win Ratio component parts: proportions of fatal perioperative bleeding events will be assessed via Fisher's exact test; and proportions of UDPB events (by category) will be assessed via a Fisher-Freeman-Halton exact test. The secondary endpoint of surgical re-exploration for bleeding will take into account time to re-exploration.

Sample Size

Approximately 120 subjects will be randomized in a 1:1 ratio to the treatment and control arms. Assuming a 5% dropout rate, at total of 114 subjects (57 per arm) are expected to be evaluable for effectiveness and safety. Sample size is based on assumed response rates for the primary effectiveness endpoint, and power can be calculated via an iterative simulation process with programming code available in an appendix to Redfors et al. (2019).[16] With a Finkelstein-Schoenfeld test, total of 57 subjects per arm ensures power of $>99.2\%$, using a two-sided alpha (α) of 0.05, and assuming an interim analysis for efficacy at 70% completion. Power for each of the key secondary endpoints is estimated at 96.3%, and for 24-hour chest tube drainage (mL), $>99.9\%$, based on a two-sample t-test assuming equal variance and a two-sided alpha of 0.05.

Similarly, although assuming unequal variances, power for comparisons of platelet transfusions (volume [mL]) and PRBC transfusions (volume [mL]), is estimated at 98.0% and 96.7%, respectively.

Interim Analysis

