Type I error (alpha, α) will be preserved from inflation due to multiplicity across the primary effectiveness, key secondary, and secondary endpoints via a hierarchical closed testing step-down approach. Only if preceding endpoints are declared statistically significant at the alpha 0.05 level, can further endpoints also be declared significant. The order of hierarchical testing will follow the order of primary, key secondary, and secondary endpoints as listed in the paragraph above, namely: the primary endpoint will be tested first, followed by the first key secondary endpoint (percent change in pre-CPB vs. post-CPB blood apixaban levels), followed by the second key secondary endpoint (percent change in pre-CPB vs. post-CPB blood rivaroxaban levels), followed by the first secondary endpoint (24-hour CTD), second secondary endpoint (platelet transfusions), and lastly the third secondary endpoint (pRBC transfusions).

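### The 96.3% power for each drug-removal key secondary holds only for 58 per arm, an even drug mix and full enrolment; on the planned 57 per arm, a drug at its permitted 40% share has about 91%

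*Combined protocol and SAP*

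**What the plan says.** Section 11.1 gives power for each key secondary endpoint (percent change in apixaban, percent change in rivaroxaban) as 96.3%, for a difference of 40 points with SD 40, an equal-variance two-sample t-test and two-sided alpha 0.05, "where N=29 subjects receiving apixaban with N=29 corresponding controls along with parallel numbers of subjects receive rivaroxaban and corresponding control". The synopsis, under Sample Size, gives the same figure without the per-drug numbers: "Power for each of the key secondary endpoints is estimated at 96.3%, and for 24-hour chest tube drainage".

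Section 11.1 also states that "a total of 114 subjects (57 per arm) are expected to be evaluable for effectiveness and safety". It says that the expected drug proportions, anywhere from 40% to 60%, "are not assumed to impact power or sample size". Section 6.2 enforces that range through the randomization system.

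The two drugs are not pooled for these endpoints. The synopsis says: "Drug removal will be analyzed for apixaban and rivaroxaban independently". Section 11.3 tests them second (apixaban) and third (rivaroxaban) in a fixed sequence, followed by 24-hour drainage, platelet transfusions and PRBC transfusions: "Only if preceding endpoints are declared statistically significant at the alpha 0.05 level, can further endpoints also be declared significant".

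Section 11.6 plans an efficacy interim at 40 per group and puts the probability of stopping there above 88.1%. Table 3 uses "Interim Analysis N=39" and "End of study N=56" per group.

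**The concern.** Exchangeability of the two drugs is a sound reason for expecting the mix not to matter to a pooled test. It does nothing for a t-test confined to one drug, where power depends on how many subjects took that drug. Table 3 varies the mix from 40:60 to 60:40 for the pooled Win Ratio only. Yet Section 11.1 opens by saying that the sample size is meant to give adequate power for the key secondary endpoints as well. The plan therefore makes a power claim for these tests and supports it at a single point of the range it permits.

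The position in the testing order gives this weight. A miss on apixaban blocks the rivaroxaban, drainage, platelet and PRBC claims. A miss on rivaroxaban blocks the last three. The power loss falls on whichever drug is under-represented.

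**Working it through.** **Inputs.** Difference 40 points and SD 40 (Sections 11.1 and 11.3), so d = 40/40 = 1.0; two-sided alpha 0.05; 1:1 allocation; 57 evaluable per arm (Section 11.1); drug share 40% to 60% (Section 6.2); interim at 40 per group (Section 11.6).

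**Method.** Exact power of the equal-variance two-sample t-test. With n1 and n2 per arm within a drug, df = n1 + n2 − 2, noncentrality λ = d × √(n1·n2/(n1+n2)), and power = P(|T| > t(0.975, df)), where T is noncentral t with parameter λ.

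**The plan's own figure.** 29 v 29: df = 56, λ = √(841/58) = 3.81, critical value 2.003, power 96.26%. This reproduces 96.3%. Two drugs at 29 each need 29 + 29 = 58 per arm.

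**Full enrolment, 57 per arm**

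| Share of the drug | n per arm in that drug | Split used | Power |
|---|---|---|---|
| 50% | 57 × 0.5 = 28.5 | 28 v 29 | 96.0% |
| 40% | 57 × 0.4 = 22.8 | 22 v 22 | 90.0% |
| 40% | 22.8 | 22 v 23 | 90.6% |
| 40% | 22.8 | 23 v 23 | 91.2% |
| 60% | 57 × 0.6 = 34.2 | 34 v 34 | 98.2% |

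Taking 22.8 per arm directly gives 91.0%. Going from 58 to 57 per arm costs 0.3 points; the drug mix costs about 5. On Table 3's 56 per arm, an even mix (28 v 28) gives 95.7%.

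Taking the two tests as independent, power to pass both is 0.9626² = 92.7% at 29 v 29 for each drug, and 0.9125 × 0.9822 = 89.6% at a 40:60 mix.

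**Interim stop, 40 per group, even arms within each drug, complete samples, no overrun**

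| Share of the drug | Split | Power |
|---|---|---|
| 50% | 20 v 20 | 86.9% |
| 40% | 16 v 16 | 78.1% |
| 60% | 24 v 24 | 92.4% |

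These are approximations and can move either way. Uneven arms lower them: 17 v 23 gives 86.1% and 13 v 19 gives 76.7%. Table 3's 39 per group gives 86.0% (19.5 per arm) and 77.0% (15.6 per arm). Missing samples would lower them further, and overrun subjects would raise them. Section 11.6 does not give the number of overrun subjects.

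**Sample sizes in the text.** Evaluable n per arm appears as 56 (Table 3), 57 (text) and 58 (implied by 2 × 29); interim n per group as 39 (Table 3) and 40 (Section 11.6).

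**The case against.** The best reply is that no printed figure is wrong. Section 11.1 gives 96.3% with its difference, SD, test, alpha and per-drug n, and the synopsis only shortens it. The sentence on the mix starts from exchangeability and leads into the Win Ratio inputs and Table 3, so a careful reader would apply it to the pooled primary only. This stands in part: the calculation is correct and the context points that way. But the sentence itself has no limit, and a synopsis reader sees neither the 29 v 29 nor the even mix.

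It can also be said that about 91% is ample. That stands at full enrolment. The plan sets no numerical target for the key secondaries and calls its 40% effect conservative.

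Three stronger readings are tempting, and the documents do not support them.

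- **The trial is underpowered for drug removal.** At full enrolment, power stays near 90% or more across the permitted mix.
- **The interim figures are floors, or the expected outcome.** They are not floors, since they assume even arms and complete samples. Nor do they describe the likely final data set after a stop: enrolment continues during the interim, and subjects treated and followed up meanwhile join the final analysis.
- **Apixaban, tested first, is the drug at risk.** The background data in the synopsis and Section 1.1 put apixaban ahead of rivaroxaban at about 3:2. If enrolment followed that, rivaroxaban would carry the loss and apixaban would gain.

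**Conclusion.** The point holds as one of incomplete and over-general power reporting; 96.3% is not a calculation error. It is the power for one configuration (58 per arm, 50:50, full enrolment), and the synopsis figure and the unrestricted mix statement do not hold for the key secondaries across the design the plan permits. On 57 per arm, power is about 96.0% at 50:50, and about 91% for a drug at 40% with 98% for the other.

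At full enrolment this is a modest loss. After an early stop, power is lower, about 87% per drug at 50:50 and about 78% for a drug at 40% under the stated conditions, and the plan gives no figure for that path. The actual value cannot be settled from the documents because the overrun number is not given.

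The results assume d = 1.0 with SD 40 in both arms, alpha 0.05 for each test as the plan states, close to even arms within each drug (an 18 v 28 split of 46 subjects gives 89.9%), and no missing drug-level samples beyond the 5% dropout.

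**What to change.** 1. In Section 11.1, limit the statement that drug proportions are not assumed to affect power or sample size to the pooled primary endpoint.
2. In the synopsis and Section 11.1, restate key-secondary power on the planned basis, for example: *With 57 evaluable subjects per arm, power for each key secondary endpoint is about 96% at a 50:50 drug mix; at a 40:60 mix it is about 91% for the drug contributing 40% and about 98% for the other.*
3. If early-stop power is added, give it as approximate and with its conditions: about 87% per drug at 50:50 and about 78% for a drug at 40%, with 40 per group, even arms within each drug, no missing samples and no overrun subjects. Do not word it as a minimum.
4. Use one evaluable n per arm and one interim n per group in the text, Table 3 and Section 11.6, recomputing any power figure whose n changes.

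The cost is a few sentences and aligned sample sizes. Sample size, data collection and testing order do not change. The only downside is a slightly less favourable stated power for the key secondaries.

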11.2. Analysis Populations

Enrolled subjects include all subjects who provide informed assent/consent. Enrolled subjects who do not meet criteria for study eligibility are deemed screening failures and will exit the study.

The **Intent-to-Treat (ITT)** Population will include all enrolled (assented/consented) subjects who are randomized.

The **modified Intent-to-Treat (mITT)** Population will include all randomized subjects who undergo the index surgical procedure **and** receive a study device (whether DrugSorb-ATR or *sham*). The main primary analyses of the trial will be performed in the mITT Population.

Baseline demographic and clinical variables will be summarized for each of the treatment groups for the ITT and mITT populations. So long as the ITT and mITT populations are not identical, the ITT subjects who do not fall within the mITT population will be presented in a listing, including the reasons for why they did not receive a study device.

The **Per Protocol (PP)** Population will include all mITT subjects who have no major protocol violations. Analysis of the primary efficacy endpoint will be performed in the PP population as a sensitivity analysis.

The **Safety Analysis (SA)** Population will include all enrolled subjects who are treated or attempted treatment with a study device. “Attempted treatment” refers to any subject(s) who initiate treatment with a study device (whether DrugSorb-ATR or *sham*) during the index procedure but experience early discontinuation of treatment due to device deficiency, clinical judgement on the part of the investigator, adverse event, or other rationale. All safety analyses will be performed in the Safety Analysis population.

